#### Time to reduction of VNRS pain score of 10 points (up to 120 minutes)

The time in minutes will be determined for the VNRS pain score (0-100) to be reduced by 10 points following randomized assignment administration for patients, when feasible.

Cognitive function at 30 minutes using Six Item Screener (SIS): The SIS will be used to detect cognitive impairment (e.g., sleepiness, confusion, memory impairment and reaction time)

at 30 minutes. Using a cutoff of  $\leq$  4 (out of 6) to reflect cognitive impairment has been proposed for ED use and has been used in prior studies of treatment of acute pain with sufentanil in the ED.

Healthcare Professional Global Assessment (HPGA) of the Method of Pain Control at 30 minutes: The HPGA of the method of pain control will also be reported by the healthcare professional (primarily nurses) at the 30-minute time period as the PGA above.

Acceptability to health care providers survey: An acceptability to health care providers score will be requested of health care providers in the ED including ED nurse, ED trauma team member and/or trauma surgery team member at 30 minutes or when feasible. The score (-2 to +2; 5-point scale) ratings will be from; very dissatisfied, dissatisfied, neither satisfied nor dissatisfied, satisfied, very satisfied, and will document providers assessment regarding the individual patient's pain management process, ease and acceptability relative to past experiences, when feasible.

Predefined Subgroups: Predefined subset analyses will be performed on: sex (male/female), Injury Severity Score (ISS  $< or \ge 16$ ), age ( $< or \ge 50$ ), blunt versus penetrating injury, history of pre-injury opioid use (Y/N), air versus ground prehospital transport, transport origin (scene versus outside ED).

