# AIM #4: To determine if, among injured patients with moderate to severe pain, treatment with DSUVIA compared to standard care pain treatment in the ED improves Healthcare Professional Global Assessment (HPGA) of the Method of Pain Control and health care provider survey scores.

Scores to the HPGA will be based on a four-point scale. A 2x4 chi-square test will be used to compare the distribution of scores across the two treatment groups. An ordinal polytomous logistic regression model will be used to compare the distribution of proportions after controlling for stratification (sites) and baseline characteristics not balanced through random assignment. The same analysis will be repeated on the health care provider survey scores, with the modification to account for a five-level outcome.

**Sample Size**: The sample size calculations are based on the analyses of the primary aim (Aim 1) of the study. To detect a minimum effect size of 0.45, a sample size of 150 subject is needed (75 per group), assuming a type I error of 0.05, a two-sided alternative hypothesis, and 80% power. Thus, assuming a standard deviation of 21 (Karcioglu, 2003), a difference of 7.1 can be detected between the mean VNRS scores.

**Missing data**: Every attempt will be made to minimize the amount of missing data. Give the short timewindow to collect data, missing data should be minimal. However, in the event that there is missing data for the outcomes, the pattern of missingness will be evaluated. Assuming that the data will be missing at random, multiple imputation techniques will be used to impute data and carry out the proposed analyses.

**Subgroup**: Analyses will be carried out for pre-defined subgroups, specifically: sex (male/female), Injury Severity Score (ISS < or  $\ge 16$ ), age (< or  $\ge 50$ ), blunt versus penetrating injury, history of prior opioid use (Y/N), air versus ground prehospital transport, transport origin (scene versus outside ED). For all subgroup analyses, regression models will be used to assess if there is a differential treatment effect by subgroup. Regression models will include main effects for treatment and the indicator of the subgroup, as well as the two-way interaction between treatment and the subgroup indicator. A statistically significant interaction will indicate a differential treatment effect.

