The DSMB will review the primary and secondary outcomes bi-annually. Prior to initiation of the trial, the final monitoring plan will be developed to serve as the guide to the DSMB's decision-making process concerning early stopping of the trial. The interim analysis will consist of two components, efficacy evaluation and futility evaluation. The purpose of the efficacy evaluation is to detect early sign of treatment effect early in the study. The purpose of the futility analysis is to assess if the study is unlikely to achieve a statistically significant effect. In making the decision to recommend termination of the study, the DSMB shall be guided by several types of information: (i) a formal stopping rule based on the primary analysis (comparison of treatment groups on the primary outcome), (ii) information on safety outcomes by treatment group, (iii) consistency between results for primary and secondary outcomes, (iv) consistency of treatment effects across subgroups, and (v) conditional power.

We have designed this trial with one-interim analyses before the final analysis. The number of interim analyses will be finalized in discussion with the DSMB prior to the initiation of the study. The interim analysis plan is based on the Lan and Demets approach utilizing an O'Brien-Fleming spending function to

determine alpha spending and test boundaries. A formal interim analysis of efficacy will be performed when 50% of the randomly assigned participants have completed the assessment of the primary outcome. We will use a t-test to test for difference. The level of significance will maintain an overall p-value of 0.05 according to O'Brien-Fleming stopping boundaries leaving a p value of 0.003 and 0.049 for the interim and final analyses, respectively. This translates to a two-sided z-value for the interim and final analyses of +/-2.96 and +/-1.97, respectively.

In addition, the futility of the study will be evaluated at the time an interim efficacy test is conducted. Specifically, the conditional power will be calculated. If the condition power is less than value prespecified by the DSMB (e.g., <20%), we can conclude that it would be futile to continue with the investigation.

Surveillance for Outcomes and Data Elements: Data will be collected prospectively as patient care progresses. This will include a review of the prehospital patient care report(s), ED and electronic/ paper hospital records.

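### Seven unadjusted interaction tests are read as establishing subgroup differences: about a 25–30% chance of at least one false claim if alpha is 0.05, with little power for real ones

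*Combined protocol and SAP*

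**What the plan says.** Section IV (Predefined Subgroups) and the Subgroup paragraph of section VI list the same seven factors, each with two levels: sex, Injury Severity Score cut at 16, age cut at 50, blunt or penetrating injury, opioid use before the injury, air or ground transport, and transport from the scene or from another ED.

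The analysis is the same for each factor: "Regression models will include main effects for treatment and the indicator of the subgroup, as well as the two-way interaction between treatment and the subgroup". The paragraph closes with the rule for reading the result: "A statistically significant interaction will indicate a differential treatment effect".

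The outcome or outcomes to be modelled are not named. No alpha is attached to the interaction tests. The only significance levels in the document concern the primary aim: the Sample Size paragraph is worked out "assuming a type I error of 0.05, a two-sided alternative hypothesis, and 80% power", and the Interim Analyses paragraph splits that level, "leaving a p value of 0.003 and 0.049 for the interim and final analyses, respectively". Nothing in the document adjusts the seven tests for multiplicity or describes them as exploratory.

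**The concern.** The closing sentence is an interpretation rule, so this is more than silence about multiplicity. Followed literally, it lets one significant result out of seven support a statement that DSUVIA works differently by, say, sex, age or transport mode. Seven chances at a conventional threshold make such a statement fairly likely even if the effect is the same in everyone.

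The trial is also sized for a main effect. An interaction is estimated much less precisely than a main effect from the same 150 patients. A result that clears the threshold must therefore be large, and will tend to exaggerate any true difference. At stake is a misleading subgroup statement in the report.

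**Working it through.** **Inputs.**
- Seven interaction tests, 1 degree of freedom each (section IV, Predefined Subgroups; section VI, Subgroup).
- 75 per arm, SD 21, standardized effect 0.45 (section VI, Sample Size).
- Alpha 0.05 two-sided for each interaction test. This is an assumption: it is the only overall type I error the plan gives, and the plan gives it for the primary aim.
- One outcome and no true interaction. Both are assumptions.
- Subgroup splits of 50/50 and 20/80. Both are assumptions; the plan gives no expected subgroup sizes.

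**The plan's own figures.** The plan states no error rate for the subgroup tests, so there is none to reproduce. The comparator is the main effect. An effect size of 0.45 at SD 21 is 0.45 × 21 = 9.45 points, but the Sample Size paragraph prints 7.1, and 7.1/21 = 0.338. The two do not agree. I use 9.45 because it follows from the stated effect size and SD, and because, as the larger value, it is the more lenient comparator here. By the normal approximation, 75 per arm gives 78.7% power for an effect size of 0.45, close to the planned 80%.

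**Chance of at least one false interaction.**
- Independent tests at 0.05: 1 − 0.95^7 = 0.302.
- At the 0.049 final-look level instead: 1 − 0.951^7 = 0.297.
- Upper bound under any dependence: 7 × 0.05 = 0.35.
- Two independent outcomes, hence 14 tests: 1 − 0.95^14 = 0.512.

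**Dependence between factors.** The factors overlap, the two transport factors especially, so I rely on a simulation: 150 patients, 1:1 allocation, one linear interaction model per factor, no true effects, 6,000 replicates per setting. Assumed prevalences were 0.35, 0.30, 0.40, 0.20, 0.25, 0.40 and 0.35. Correlations are those of the underlying normal variables.

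| Assumed correlation | At least one p < 0.05 |
|---|---|
| None | 29.3% |
| Transport pair 0.7, others 0 | 29.2% |
| All 0.3, transport pair 0.8 | 28.0% |
| All 0.6, transport pair 0.9 | 24.5% |

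The Monte Carlo standard error is about √(0.3 × 0.7/6000) = 0.6 percentage points.

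**Precision of one interaction.** With a fraction f of each arm in one level, SE = 21 × √(2/(75f) + 2/(75(1 − f))).
- f = 0.5: 21 × √(0.0533 + 0.0533) = 6.86.
- f = 0.2: 21 × √(0.1333 + 0.0333) = 8.57.

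| Quantity | 50/50 split | 20/80 split |
|---|---|---|
| Detectable with 80% power, (1.96 + 0.84) × SE | 19.2 points | 24.0 points |
| Smallest estimate reaching p < 0.05, 1.96 × SE | 13.4 points | 16.8 points |
| Power for a true interaction of 9.45 points | 28% | 20% |

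At these standard errors an estimate must be at least 13.4 points in size to be significant. A true interaction of 9.45 points or less that is declared significant is therefore overestimated, or has the wrong sign. For a true 9.45 points and an even split, significant estimates in the right direction average about 1.9 times the truth.

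**The case against.** The case for leaving the text alone has real substance. The subgroups are fixed in advance and few in number, and the plan uses interaction tests instead of comparing p-values within subgroups. Each test, taken alone, keeps its own error rate; 30% is a family-wise figure for secondary analyses. No aim or hypothesis concerns subgroups, and section IV calls the study a pilot. All of that stands, and it limits the seriousness of the point. It does not change what the closing sentence permits.

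Four stronger readings are tempting, and the documents do not support them.

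- **That the plan sets p < 0.05 for these tests and treats one as proof.** The threshold is inferred, and the plan's verb is milder than proof.
- **That a significant interaction would be mostly chance, or that real ones are undetectable.** The first depends on how common true interactions are, which the documents do not say. As to the second, power of 28% is low but not nil.
- **That the error rate carries into stopping decisions.** The Interim Analyses paragraph does list "iv) consistency of treatment effects across subgroups" among five kinds of information for the DSMB. It does not mention interaction tests or a significance rule there, and the formal stopping rule rests on the primary outcome.
- **That a multiplicity correction is required.** Bonferroni at 0.05/7 = 0.00714 would bring the family-wise rate to 4.9% under independence. For a 9.45-point interaction with an even split, however, it cuts power from 28% to about 9%, and the average exaggeration rises from about 1.9-fold to 2.3-fold. Holm's first step uses the same threshold. For secondary analyses this is a debatable trade.

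**Conclusion.** The concern holds as a fault in the interpretation rule. Taken at its word, the plan carries roughly a 25% to 30% chance of at least one false subgroup claim, given alpha 0.05, a single outcome and no true interaction. The lower end needs strongly correlated factors. Using 0.049 changes nothing material, and modelling more outcomes would raise the figure. The detectable interaction is about two to two and a half times the 9.45-point main effect (19.2/9.45 = 2.0; 24.0/9.45 = 2.5), so the tests cannot bear the weight the sentence gives them. The power figures assume SD 21, 75 evaluable patients per arm and the two splits shown.

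The primary analysis, the sample size and the formal stopping rule are untouched. This is an inexpensive improvement to what the trial may conclude, and does not call the design into question.

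**What to change.** Replace the last sentence of the Subgroup paragraph in section VI with:

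> Interaction estimates with 95% confidence intervals will be reported for all seven subgroups; these analyses are exploratory, are not adjusted for multiplicity, and a nominally significant interaction will be treated as hypothesis-generating and not as evidence establishing a differential treatment effect.

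Holm-adjusted p-values may be shown alongside, but need not be.

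The cost is one sentence, with no new data, patients or change of design. The trial gives up firm subgroup claims, which it has little power to support.

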## VII. Clinical Coordinating Center (CCC)

Clinical Coordination specific to the DEEP study will be performed by the LITES Network Coordinating Center and their dedicated research team at the University of Pittsburgh, including all regulatory requirements, provider and coordinator training and monitoring.

## VIII. Data Coordinating Center (DCC)

Data Coordination specific to the DEEP study will be performed by the DCC and led by [name] at the Graduate School of Public Health at the University of Pittsburgh. The DCC will coordinate all data collection and entry, management, security and confidentiality, data archiving, quality control and electronic medical record biomedical informatics as needed, as well as plan, coordinate and assist with all statistical analyses.

## IX. Human Subjects

We anticipate that this study will be conducted utilizing a written informed consent while the patient resides in the ED.

Study Risks and Benefits: Risks associated with pain management include allergic reaction, hypoxia requiring oxygen, (SPO2 < 90%), hypotension (SBP < 90 mmHg), or need for advanced airway management (placement of an endotracheal tube or supraglottic airway) following medication administration.

Regardless of treatment arm, we anticipate that enrolled subjects will benefit from increased monitoring of primary and secondary outcomes, specifically, a focus on adequate pain control and pain management complications including respiratory compromise, hypotension, decreased sensorium, and need for advanced airway control.

Institutional Review Board: A central IRB at the University of Pittsburgh will be utilized for the regulatory needs of studies. All current LITES Network sites have IRBs which have experience and engagement with central IRB procedures.

Training and Participating Site Coordination: As the clinical coordinating center for the trial, the University of Pittsburgh (LITES) at the University of Pittsburgh will be collaboratively responsible for all research coordinator training, provider training. Research coordinators, providers and associated staff will be trained during the months prior to the trial start date regarding the scientific basis for the study, specific inclusion and exclusion criteria, study procedures and SOPs. Training verification and retraining will occur if new staff is hired at individual participating sites.

## X. Safety Monitoring

#### Adverse Event and Non-compliance definitions

- a. *Adverse event* means any untoward medical occurrence associated with the use of the drug in humans, whether or not considered drug related.
- b. *Adverse reaction* means any adverse event caused by a drug. Adverse reactions are a subset of all suspected adverse reactions where there is reason to conclude that the drug caused the event.

- c. *Suspected adverse reaction* means any adverse event for which there is a reasonable possibility that the drug caused the adverse event. Suspected adverse reaction implies a lesser degree of certainty about causality than "adverse reaction"
- d. *Reasonable possibility*. For the purpose of safety reporting, "reasonable possibility" means there is evidence to suggest a causal relationship between the drug and the adverse event.
- e. *Unexpected adverse event/reaction* refers to an event/reaction that is not consistent with the risk information described in the package insert and general investigational plan.
- f. *Life-threatening, suspected adverse reaction*. A suspected adverse reaction is considered "life-threatening" if, in the view of either the Investigator (i.e., the study site principal investigator) or Sponsor, its occurrence places the patient or research subject at immediate risk of death. It does not include a suspected adverse reaction that had it occurred in a more severe form, might have caused death.
- g. *Serious, suspected adverse reaction.* A suspected adverse reaction is considered "serious" if, in the view of the Investigator (i.e., the study site principal investigator) or Sponsor, it results in any of the following outcomes: death, a life-threatening adverse reaction, inpatient hospitalization or prolongation of existing hospitalization, a persistent or significant incapacity or substantial disruption of the ability to conduct normal life functions, or a congenital anomaly/birth defect.
- h. *Reportable non-compliance* refers to a failure on the part of the investigator or study team member to follow the terms of the IRB approved protocol or abide by applicable laws or regulations, that adversely affect the rights and welfare of subjects or significantly compromises the quality of the research data. Incidents of non-compliance on the part of the subject are not considered reportable.
- i. Unanticipated Problem Involving Risk to Subjects or Others (UPIRTSO) refers to any accident, experience, or outcome that meets the following criteria: unexpected in terms of nature, severity or frequency; related, or possibly related, to a subject's participation in research; and places subjects or others at greater risk of harm (including physical, economic, or social) than was previously known or recognized.

Assessing and Reporting Adverse Events (AEs) and Non-compliance: Adverse events will be reviewed by the study sites and assessed for relationship to the study intervention. Investigators and study team will determine if any related adverse events occur during the period from enrollment through study participation termination. If reportable adverse events occur, they will be recorded on the adverse event case report form in the electronic data capture system, which will be submitted to the Coordinating Center. All reported adverse events will be classified by: a) Severity (fatal or life-threatening, serious, or non-serious); and b) Expected vs. Unexpected. An event will be determined to be unexpected if it is not consistent with the risks identified in the package insert or with the information provided in the general investigational plan. Please refer to the table below for timelines for reporting.

This study population is expected to have a relative low number of serious adverse events but will include death from trauma related injuries. Expected adverse events that are related or possibly related to the intervention will be documented and reviewed for changes in nature, severity, or frequency across the study population.

Organization	Unexpected, fatal or life-threatening suspected adverse reactions	Unexpected, serious, suspected adverse reactions	Expected adverse reactions	Reportable non- compliance	UPIRTSO
IRB	24 hours	10 working days	No reporting	10 working days	10 working days
Dept. of Defense	30 calendar days	30 calendar days	No reporting	30 calendar days**	30 calendar days*
DSMB	24 hours	7 calendar days	At next meeting (every 6 months)	At next meeting (every 6 months)	14 days*

\*reported based on IRB determination that event is UPIRTSO \*\*reported based on IRB determination that non-compliance is serious or continuing

Data Safety Monitoring Board (DSMB): A Data and Safety Monitoring Board (DSMB) will be created to review this study and provide recommendations regarding study continuation to the Sponsor. After initial approval and at periodic intervals (to be determined by the committee) during the course of the study, the DSMB responsibilities are to:

a. Review the research protocol, informed consent documents and plans for data and safety monitoring;

b. Evaluate the progress of the study, including periodic assessments of data quality and timeliness, participant recruitment, accrual and retention, participant risk versus benefit, adverse events, unanticipated problems, performance of the trial sites, and other factors that can affect study outcome;

c. Consider factors external to the study when relevant information becomes available, such as scientific or therapeutic developments that may have an impact on the safety of the participants or the ethics of the study;

d. Review clinical center performance, make recommendations and assist in the resolution of problems reported by the study site Investigators;

e. Protect the safety of the study participants;

f. Report on the safety and progress of the study;

g. Make recommendations concerning continuation, termination or other modifications of the study based on the observed beneficial or adverse effects of the treatment under study;

h. Monitor the confidentiality of the study data and the results of monitoring;

i. Assist by commenting on any problems with study conduct, enrollment, sample size and/or data collection.

j. The DSMB will include experts in emergency medicine, surgery (trauma/critical medicine), bioethics and biostatistics. Members will consist of persons independent of the investigators who have no financial, scientific, or other conflict of interest with the study. Written documentation attesting to absence of conflict of interest will be required.

k. The University of Pittsburgh Office of Clinical Research, Health Sciences will provide the logistical management and support of the DSMB. A safety officer (chairperson) will be identified at the first meeting. This person will be the contact person for serious adverse event reporting. Procedures for this will be discussed at the first meeting.

1. The first meeting will take place before initiation of the study to discuss the protocol, approve the commencement of the study, and to establish guidelines to monitor the study. The follow-up meeting frequency of the DSMB will be determined during the first meeting. An emergency meeting of the DSMB will be called at any time by the Chairperson should questions of patient safety arise.

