#### Exclusion Criteria

1. Advanced airway management prior to 1st dose administration

- 2. Known allergy to fentanyl, sufentanil, or meperidine
- 3. Known prisoner
- 4. Known pregnancy
- 5. ED pain treatment contraindicated
- 6. Estimated BMI >40
- 7. Significant respiratory depression
- 8. Known or suspected gastrointestinal obstruction, including paralytic ileus

Study Intervention: The study intervention will be the administration of 30 micrograms of DSUVIA in tablet form utilizing a sublingual applicator following informed consent for participation.

Study Intervention Arm: Patients randomized to the study intervention arm will receive DSUVIA via approved applicator as soon as feasible after randomization. A single dose of DSUVIA will be provided as directed on the package insert. Pre-randomization pain treatment will not be prohibited for study participation and dosage and narcotic type will be documented and recorded.

Standard Care Arm: Patients randomized to the standard care arm will receive standard care pain management. Dose administered and the respective narcotic will be recorded. Pre-randomization pain treatment will not be prohibited for study participation and dosage and narcotic type will be documented and recorded.

Randomization and Masking: Individual patients meeting all inclusion and no exclusion criteria in the emergency department will be randomized and assigned according to a 1:1 ratio of DSUVIA or standard care pain treatment using a permuted block design with variable block sizes of 4 and 6. A predefined randomization assignment will be utilized. The arm assignment will be provided in real time at the individual patient level. Trauma attending and ED physicians will not be masked to treatment assignment as the study intervention will not be blinded. Arm assignment will be concealed to all outcome assessors for follow up.

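### The AE form is filtered on relatedness to DSUVIA and on an undefined term, so events outside the prespecified safety outcomes have no clear arm-neutral route onto it

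*Combined protocol and SAP*

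**What the plan says.** The rule is in Section X, Assessing and Reporting Adverse Events (AEs) and Non-compliance, and has three steps. Sites make a causality judgement: "Adverse events will be reviewed by the study sites and assessed for relationship to the study intervention". They look for events that pass it: "Investigators and study team will determine if any related adverse events occur during the period from enrollment through study participation termination". The entry rule follows: "If reportable adverse events occur, they will be recorded on the adverse event case report form in the electronic data capture system". That form is what goes to the Coordinating Center.

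Section III, Study Intervention, fixes the term on which the first step turns: "The study intervention will be the administration of 30 micrograms of DSUVIA in tablet form utilizing a sublingual applicator". Standard care is described separately, with the choice of narcotic left open.

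Item a of the Section X definitions is wider than the rule. It covers "any untoward medical occurrence associated with the use of the drug in humans, whether or not considered drug related".

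A second stream of safety data exists. Section IV makes the following secondary outcomes in both arms: hypoxia, hypotension, advanced airway or bag-mask ventilation, and treated nausea, vomiting, headache or dizziness. Section VI, Aim 2, compares them between arms. Section VI, Interim Analyses, has the DSMB review secondary outcomes bi-annually and lists "information on safety outcomes by treatment group" among the things that guide a recommendation to stop.

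**The concern.** The definition of an AE ignores causality, but the recording rule appears to require it, and to require it against one arm's drug. A patient given a standard-care opioid has not received DSUVIA, so on a literal reading nothing that happens to that patient can be related to the study intervention. In the DSUVIA arm, entry depends on attribution in an open-label trial, among trauma patients whose injury is nearly always another possible cause.

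Two things are at stake. AE-form counts could differ between arms because of how they were recorded, not because of the drugs. And a DSUVIA event attributed to injury might never reach the form.

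**Working it through.** The documents give no AE rate, AE power or recording fraction, so there is no stated figure to reproduce. The check is to trace kinds of event through the text.

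| Event | Outcome stream (Section IV) | AE form, DSUVIA arm | AE form, standard-care arm (literal reading) |
|---|---|---|---|
| SpO2 < 90%, SBP < 90 mmHg, airway device or bag-mask ventilation, to ED discharge or 120 minutes | Counted in both arms, no relatedness test | Not needed for the comparison | Not needed for the comparison |
| Nausea, vomiting, headache or dizziness, treated, first 30 minutes | Counted in both arms, no relatedness test | Not needed for the comparison | Not needed for the comparison |
| Same symptoms, untreated or after 30 minutes | Outside the definition | If judged related and reportable | No stated route |
| Allergic reaction (a named risk in Section IX) | Not an outcome | If judged related and reportable | No stated route |

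The first two rows bypass the filter. The last two depend on it.

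Four further pieces of Section X were set beside the rule:

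- *Reportable* is defined for non-compliance (item h) but not for AEs.
- Expectedness is judged against the package insert or the general investigational plan. The only insert mentioned elsewhere is DSUVIA's (Section III, Study Intervention Arm). No reference is named for the standard-care narcotics.
- Expected events are to be documented when they are related, or possibly related, to the intervention.
- The AE columns of the reporting table cover only suspected adverse reactions and adverse reactions. The 24-hour and 7-calendar-day alerts to the DSMB therefore require a causal judgement first. The unfiltered outcome stream is reviewed only bi-annually.

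All four point the same way as the literal reading.

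The mechanism can be written down, though not sized. With n patients per arm, true event rate r and recorded fraction c, the expected number on the form is n × r × c. If r is equal in both arms, the ratio of the two counts is c(DSUVIA) / c(standard care), whatever r is. Only n = 75 comes from the plan (Section VI, Sample Size). The rest are assumptions, shown to give a range:

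- r = 2%, c = 0.8 for DSUVIA and 0.1 to 0.8 for standard care: 75 × 0.02 × 0.8 = 1.2 against 0.15 to 1.2.
- r = 10%, same fractions: 75 × 0.10 × 0.8 = 6.0 against 0.75 to 6.0.

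Equal recording gives equal expected counts. Unequal recording distorts the ratio, but for rare events the counts are very small either way. This applies only to events that reach the DSMB solely through the form.

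**The case against.** The strongest reply is that the opioid harms that matter most never depend on this form. They are counted after the first post-randomization analgesic in either arm, with no causality test, and the DSMB sees them by arm. That stands, and it confines the point. It does not close it: the tolerability outcome is limited to treated symptoms in the first 30 minutes, both outcome definitions are qualified by feasibility, and allergic reaction is in neither.

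A second reply is that *intervention* is used loosely. Section IV (rescue doses) and Section VI (Interim Analyses) use it for whatever was assigned, and Section IX frames risk as that of pain management generally. So an exclusion of standard-care events is an inference, not something the plan states. That also stands. But Section X uses the term that Section III defines, and if sites can read it two ways, recording will vary by site.

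Third, unanticipated problems are tied to participation in research, which is neutral between arms. True, but such an event must be unexpected and must raise risk beyond what was known, so this is not a general route for AEs.

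Fourth, the monitoring plan and the procedures for serious-event reporting are to be settled with the DSMB and cannot be seen here. They may add protection. They cannot recover events that were never recorded.

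On masking, Section III names trauma attendings and ED physicians as unmasked and conceals assignment from outcome assessors for follow-up. Section X gives the causality call to investigators and the study team without saying whether they are masked.

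**Conclusion.** The point holds in a limited form. As written, the AE-form rule conflicts with the plan's own AE definition and gives no clear arm-neutral route for events outside the named safety outcomes or their windows, or for expedited DSMB alerts. For those events, counts from the form would not be comparable between arms. This rests on reading the study intervention as Section III defines it. The size of the effect cannot be derived from the documents.

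A reader might infer that the DSMB's safety comparison as a whole is one-sided, or that everything the DSMB receives passes through the filter. The documents do not support either reading, because the named outcomes reach it by arm and unfiltered. A reader might also infer that the rule would produce a falsely significant AE difference. No test of AE-form counts is planned. Where the DSMB's tasks mention adverse events (Section VI, Interim Analyses; Section X, DSMB), they do not specify a comparison by arm. Any such probability would rest wholly on assumed rates and recording fractions.

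The change is worth making before data accrue, because it is cheap and unrecorded events are hard to recover.

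**What to change.** Reword Section X, Assessing and Reporting Adverse Events, as follows:

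1. Record on the AE form every event that meets definition a, in both arms, over the period already stated (enrollment to the end of study participation), whatever its relatedness.
2. After recording, assess relatedness to the randomized analgesic, meaning DSUVIA or standard care, in place of the study intervention.
3. Define *reportable* for AEs, and name the reference for expectedness of the standard-care drugs.
4. Apply the reporting table after recording, to both arms.
5. Give the DSMB all-cause counts by arm first, then related counts.

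Item a ties an AE to use of *the drug*; add that this means the analgesic given in either arm, so that it agrees with Section III.

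The cost is a wording change, brief site retraining and a few more AE entries, some of which will reflect the injury and not the analgesic.
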